9.3 Vital Signs

Summary statistics for vital signs will be provided. For the double-blind treatment period, vital signs, change from baseline will be summarized for the Safety Sample by treatment group.

Potentially clinically relevant vital signs measurements identified in the double-blind treatment period for the Safety Sample will be summarized by treatment group. Criteria for identifying vital signs of potential clinical relevance are provided in [Appendix 1](#). All potentially clinically relevant events or changes will be listed and included in summary tables.

9.4 12-Lead ECG

Summary statistics and incidence of potentially clinically relevant changes will be provided for ECG parameters.

For the analysis of QT and QTc, data from three consecutive complexes (representing three consecutive heart beats) will be measured to determine average values. The following QT corrections will be used for reporting purposes in the clinical study report:

- 1) QTcB is the length of the QT interval corrected for heart rate by the Bazett formula:

$$QTcB=QT/(RR)^{0.5}$$
 and
- 2) QTcF is the length of the QT interval corrected for heart rate by the Fridericia formula:

$$QTcF=QT/(RR)^{0.33}$$
- 3) QTcN is the length of the QT interval corrected for heart rate by the FDA Neuropharm Division formula: $QTcN=QT/(RR)^{0.37}$

Potentially clinically relevant changes in the 12-lead ECG identified in the double-blind treatment period for the Safety Sample will be listed and summarized by treatment group. Criteria for identifying ECG measurements of potential clinical relevance are provided in [Appendix 3](#).

Categorical changes in ECG parameters during the double-blind treatment period will be summarized based on the following criteria:

Categorical Change Criteria in QT/QTc Parameters		
Classification	Category	Criteria
QT	New Onset (> 450 Msec)	New onset (>450 msec) in QT means a subject who attains a value > 450 msec during treatment period but not at baseline.
QTc *	New Onset (≥ 450 Msec for men and ≥ 470 Msec for women)	New onset (≥ 450 Msec for men and ≥ 470 Msec for women) in QTc means a subject who attains a

Categorical Change Criteria in QT/QTc Parameters		
Classification	Category	Criteria
	for women)	value \geq 450 Msec for men or \geq 470 Msec for women during treatment period but not at baseline.
	New Onset (\geq 450 Msec for men and \geq 470 Msec for women) And > 10% Increase	New onset (\geq 450 Msec for men and \geq 470 Msec for women) and > 10% increase in QTc means a subject who attains a value \geq 450 Msec for men or \geq 470 Msec for women, and > 10% increase during treatment period but not at baseline
	New Onset (> 500 Msec)	New onset (> 500 msec) in QTc means a subject who attains a value > 500 msec during treatment period but not at baseline.
	Increase 30 - 60 Msec	Increase from baseline value > 30 and \leq 60 msec in QTc
	Increase > 60 Msec	Increase from baseline value > 60 msec in QTc

* QTc categorical change criteria apply to QTcB, QTcF and QTcN.

9.5 Physical Examinations

By-patient listings will be provided for physical examination.

9.5.1 Body Weight, Waist Circumference and BMI

Analyses of body weight, waist circumference and BMI will be performed for the Safety Sample. The mean change from baseline-to Day 21 (OC) and last visit in the double-blind treatment period in body weight will be tabulated and analyzed using ANCOVA. The ANCOVA models for both the OC and last visit analyses will include the baseline as a covariate and the treatment group as fixed effect.

Percentages of patients showing significant weight gain (\geq 7 % increase in weight), as well as percentages of patients showing significant weight loss (\geq 7 % decrease in weight) from baseline to Day 21 (OC and LOCF) will be analyzed using CMH General Association Test.

Body mass index is defined as weight in kilograms divided by the square of height in meters.

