3.6 Measures to Minimize/Avoid Bias

During the entire trial, treatment will be double-blind. In other words, neither the investigator nor the subject will have knowledge of the treatment assignment at any given visit.

Treatment assignments will be based on a fixed-block computer-generated randomization code provided by the Otsuka Pharmaceutical Development & Commercialization, Inc. (OPDC) Biometrics Department. The randomization will be stratified by trial site and designed to allocate subjects to a treatment regimen in a 1:1 ratio. Sponsor personnel, including those involved in monitoring, data management, and data analysis, will not have access to the treatment code during the trial. Access to the treatment codes will be restricted to personnel charged with generating and maintaining randomization files, packaging IMP, operating the IWRS, and reporting serious adverse events (SAEs) to regulatory agencies.

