3.2 Trial Treatments

During the double-blind treatment phase, subjects will receive IMP consisting of brexpiprazole monotherapy or placebo, depending on the subject's treatment assignment.

As shown in Table 3.2-1, subjects will receive a starting dose of 2 mg/day of brexpiprazole (or corresponding placebo) from Days 1 to 3, followed by titration to 3 mg/day brexpiprazole (or placebo) on Day 4. Subjects may be titrated (or re-titrated) to a higher dose of brexpiprazole (or placebo), up to a maximum of 4 mg/day, based on treatment response and at the investigator's discretion anytime at Day 7 or thereafter. Subjects who are unable to tolerate their current dose can be titrated down at any time to a minimum of 2 mg/day. Dose adjustments must be made in increments of 1 mg/day. Subjects who are unable to tolerate 2 mg/day brexpiprazole will be discontinued from the trial.

Table 3.2-1 Dosing Schedule			
Dose	Days 1-3	Days 4^a	Days 7-21^b
Brexipiprazole	2 mg	3 mg	2-4 mg
Placebo	Placebo	Placebo	Placebo

^aDown titration can occur at any time due to tolerability after Day 4. The minimum dose allowed is 2 mg/day.

^bOption to titrate 2 to 4 mg (i.e., 2 mg, 3 mg, or 4 mg) based on clinical response and tolerability; changes must occur in 1 mg/day increments. Increases up to 4 mg/day may occur no earlier than Day 7.

All doses of IMP should be taken at the same time each day, if possible, and can be taken without regard to meals. If tolerability issues arise, the timing of administration of the IMP may be adjusted at the investigator's discretion in order to achieve optimum tolerability and compliance. Subjects will be counseled on the importance of taking the IMP.

4 Sample Size and Power Justification

It is anticipated that approximately 320 subjects will be randomized from an estimated 45 sites in the US and Europe. The primary efficacy endpoint is the change from baseline to Day 21 in the double-blind treatment phase in the YMRS Total Score. The trial will compare the placebo arm to the brexpiprazole arm, randomized at a ratio of 1:1, with an overall significance level of 0.05 (2-sided) for the primary endpoint.

CCI

CCI

The planned sample size of 304 evaluable subjects (152 in each treatment arm) will yield at least 90% power to detect the treatment effects at a 2-tailed significance level of 0.05.

A sufficient number of subjects will be enrolled and randomized to achieve approximately 304 evaluable subjects in the double-blind treatment phase CCI

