**8.1.4 Subgroup Analyses**

Subgroup analyses of change from baseline in YMRS Total Score to every study week in the double-blind treatment period will be performed by the following factors:

- Sex (Based on the biological status)
- Race (White and All Other Races)
- Age group (Age<55 and Age≥55)
- Region (North America and Europe)

All subgroup analyses will be conducted using the same MMRM analysis as for the primary efficacy analysis except that the fixed class effect term for trial center will not be included in the model

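### The body-weight ANCOVA omits trial site, the randomization stratum; if weight change differs between sites, its standard error is somewhat too large and the test conservative

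*SAP*

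**What the plan says.** On the weight model, SAP 9.5.1 states that the ANCOVAs for both the observed-case and last-visit analyses "will include the baseline as a covariate and the treatment group as fixed effect". On the population: "Analyses of body weight, waist circumference and BMI will be performed for the Safety Sample". The same section also compares the proportions with a weight gain or loss of at least 7% by a CMH test.

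On allocation, Protocol 3.6 states: "The randomization will be stratified by trial site and designed to allocate subjects to a treatment regimen in a 1:1 ratio". It adds: "Treatment assignments will be based on a fixed-block computer-generated randomization code". The block size is not given. SAP section 4 expects that "approximately 320 subjects will be randomized from an estimated 45 sites in the US and Europe".

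The term list of the primary MMRM in SAP 8.1.1 is blacked out. SAP 8.1.4 shows that it includes center, because the subgroup models are the same "except that the fixed class effect term for trial center will not be included in the model".

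The visible text gives no power or precision target for weight, no between-site variance for weight change, and no reason for leaving site out of the weight model.

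**The concern.** Blocking 1:1 within site nearly balances the arms at each site, so site differences in weight change largely cancel from the treatment difference. A model without site does not know this. It counts the between-site variance as residual noise and reports a standard error larger than the real sampling variability of the estimate.

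For an efficacy endpoint a conservative test mainly costs the sponsor power. For a safety endpoint it costs the reader: an interval that is too wide makes a real weight effect harder to see. The plan appears to follow the stratification in its primary model but not here, although the weight analysis uses the whole Safety Sample.

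**Working it through.** The plan has no figure for weight to reproduce, so the check asks how far the planned standard error can be from the true one.

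**Inputs from the documents.** 320 randomized, 160 per arm; about 45 sites (320/45 = 7.1 per site); 1:1 fixed blocks within site; model terms as in SAP 9.5.1.

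**Assumptions.** Share of weight-change variance lying between sites (ICC) of 0 to 20%; block size 4; uneven site sizes; a 0.3 SD treatment difference for power; two-sided 5% level, which the SAP states in its efficacy section and does not restate for weight.

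**Closed-form approximation.** Set the total SD to 1 and take arms as exactly balanced within sites.

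- Planned SE = √(2/160) = 0.1118, whatever the ICC.
- True SE under site-stratified allocation = √((1 − ICC) × 2/160).
- Ratio = 1/√(1 − ICC), which is 1.00, 1.026, 1.054 and 1.118 at ICC 0, 0.05, 0.10 and 0.20.
- The planned test rejects when the estimate exceeds 1.96 × 0.1118 = 0.219 in absolute value. At ICC 0.20 the true SE is √(0.80 × 0.0125) = 0.100, so type I error is 2 × (1 − Φ(2.19)) = 2.8%. Power at 0.3 SD is Φ((0.3 − 0.219)/0.100) = 79.1%, against Φ(0.3/0.100 − 1.96) = 85.1% for a model that uses the correct SE.

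**Simulation of a random site intercept** (REML, 4000 trials per setting, 320 subjects, 45 uneven sites, blocks of 4). This allows for incomplete blocks and for estimating the site variance.

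| ICC (assumed) | Planned SE / random-site SE | Power at 0.3 SD, planned | Power at 0.3 SD, random site |
|---|---|---|---|
| 0 | 1.005 | 76.6% | 76.8% |
| 0.02 | 1.011 | 77.0% | 77.6% |
| 0.05 | 1.023 | 76.8% | 78.3% |
| 0.10 | 1.049 | 76.9% | 79.8% |
| 0.20 | 1.107 | 78.6% | 85.0% |

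Type I error of the planned test was 4.0% at ICC 0.10 and 2.9% at 0.20; with the random intercept it was 4.8% and 4.9%. Monte Carlo error is about √(0.77 × 0.23/4000) = 0.7 points on power and √(0.05 × 0.95/4000) = 0.3 points on type I error. At ICC 0.10 the two estimators had nearly the same empirical SD (0.1068 and 0.1063). The gap is therefore mostly a misstated standard error, not a less efficient estimate.

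**Fixed site effects instead** (3000 trials per setting, 320 or 250 subjects, equal or uneven sites). The width of the planned interval divided by that with fixed site effects was 0.97 to 0.99 at ICC 0, 0.98 to 1.00 at 0.02, 1.00 to 1.02 at 0.05, 1.02 to 1.04 at 0.10 and 1.08 to 1.10 at 0.20. With about 7 subjects per site, fixed effects break even at an ICC of about 0.02 to 0.05. Below that they make the interval up to about 3% wider (1/0.974 = 1.027).

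**The case against.** The strongest objection is that the documents do not show that weight change varies between sites at all. A reader might infer that the planned interval is certainly too wide, or that the trial will miss weight gain. Neither follows. Every figure above depends on an assumed ICC, and near zero there is nothing to gain. This stands, and the point is conditional for that reason.

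The protocol also limits the likely sources of site variation. Section 3.7.3.3.2 asks for calibrated scales, the same scale for each subject where possible, and standard weighing conditions; a constant scale offset cancels in a change score. Section 3.1 keeps all subjects in hospital for at least the first 2 of 3 weeks. This stands in part. Hospital diet and the investigator's decision on discharge for the last week can still differ by site.

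A third argument is that the plan drops center knowingly in the subgroup models, so a simpler model is an accepted choice. That carries little weight: the subgroup models split sites that are already small, and the weight model does not. It is fair, however, that center is a fixed effect in the primary model and that copying that form could lose precision here. The objection bears on the form of the term, not on including site.

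Finally, a reader might call this the only model-based treatment test among the safety outcomes. That cannot be checked, because SAP 9.6 is blacked out. The visible text attaches no testing hierarchy or decision rule to weight, and the CMH test of changes of at least 7% is a separate comparison not examined here.

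**Conclusion.** The point holds in conditional form. The weight ANCOVA omits the factor on which randomization was stratified, and the visible text gives no reason. If sites differ in 3-week weight change, the planned standard error overstates the true one: by about 2% at a between-site share of 5%, 5% at 10% and 11% at 20%, with about 0.5% at zero. The power loss at 0.3 SD runs from about nil to about 6 points with 320 subjects, and type I error falls to about 3% at the top of the range.

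It would be wrong to read this as bias or as an invalid analysis. The estimate is unbiased and the error is conservative, so false positives are not inflated. The sizes rest on the assumed ICC range, block size, site-size distribution and effect. They also use all 320 randomized subjects, whereas the Day 21 observed-case analysis may have fewer. That the primary model includes center is inferred from SAP 8.1.4. This is a free improvement to a safety analysis, not a defect that puts a conclusion at risk.

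**What to change.** In SAP 9.5.1, add trial site, as used to stratify the randomization, as a random intercept in both the observed-case and the last-visit ANCOVA. Keep baseline weight as covariate and treatment as fixed effect. Use a random and not a fixed term, because about 45 fixed site effects could cost up to about 3% in precision if sites do not differ.

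The cost is one model term and no new data. In the simulation the random intercept lost no material precision at any ICC, including zero. Make the change before unblinding, so that the choice is not made after the weight results are known.

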9.6 CCI

9.7 Suicidality Data

Suicidality will be monitored during the study using the C-SSRS and will be summarized as number and percentage of subjects reporting any suicidal behavior, ideation, behavior by type (4 types), ideation by type (5 types) and treatment emergent suicidal behavior and ideation. Summary will be provided for the double-blind treatment period.

Suicidality is defined as report of at least one occurrence of any type of suicidal ideation or at least one occurrence of any type of suicidal behavior during assessment period (count each person only once).

Treatment emergent suicidal behavior and ideation is summarized by four types: Emergence of suicidal ideation, Emergence of serious suicidal ideation, Worsening of suicidal ideation, Emergence of suicidal behavior.

Emergence of suicidal behavior/ideation is defined as report of any type of suicidal behavior/ideation during treatment when there was no baseline suicidal behavior/ideation.

Emergence of serious suicidal ideation is defined as observation of suicidal ideation severity rating of 4 or 5 during treatment when there was no baseline suicidal ideation.

Worsening of suicidal ideation is defined as a suicidal ideation severity rating that is more severe than it was at baseline.

9.8 Concomitant Medications

Number and proportion of patients taking concomitant medications prior to study therapy, during the double-blind treatment period, and after study therapy are tabulated by drug classification using the WHO drug dictionary.

9.9 Extent of Exposure

The start date of double-blind study therapy - brexpiprazole or placebo - will be the first day of double-blind dosing. The number and percentage of patients who receive double-blind study medication, will be presented by week and by treatment group. Each dosing week will

be based on the actual week; i.e., Day 1-7 in Week 1, Day 8-14 in Week 2, etc. This summary will be performed on the Safety Sample.

The mean daily dosage will be summarized by week and treatment group using descriptive statistics. The mean daily dosage per patient per week will be determined for each week of the study. This will be calculated by dividing the sum of individual total doses by the number of days in the week interval. The summary will contain for each treatment group the number of patients receiving double-blind study medication^a, and the mean and range of the mean daily dose for each week.

10 Conventions

10.1 Study Visit Windows

Study visit windows will be used to map visits using study day intervals. Observations at each scheduled visit and Early Termination will be assigned to Day 4, Day 7, Day 14 and Day 21 visits based on their visit windows as shown in Table 10.1A. This visit window convention applies to tables and listings for all efficacy and safety scales (YMRS, CGI-BP, CCI [REDACTED])

[REDACTED] This derived study window variable will be named as DAY and will be footnoted. In listings, it will be listed along with the CRF study visit.

[figure not shown]
Table 10.1A shows classifications for study day intervals in the double-blind period. The variable “target day” is defined using the number of days since the start of double-blind dosing. The first day of double-blind dosing is defined as “Day 1”.

If more than one observation falls within a particular study day interval, then the last observation within that interval is used. Evaluations occurring more than 7 days after the last double-blind dosing date will not be mapped into study visit windows, and will be excluded from the analysis.

Table 10.1A: Study Day and Visit Windows

Day	Target Day ^a	Study Day Interval ^a
4	4	2-5
7	7	6-10
14	14	11-17
21	21	18-24 ^b

^a Relative to the first day of IMP in the double-blind treatment period.

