Treatment Phase: Following the screening period, subjects who meet all inclusion criteria, including a score of ≥ 24 on the Young-Mania Rating Scale (YMRS)⁸ at screening and baseline, and meet none of the exclusion criteria, will be randomized in a 1:1 ratio to receive either placebo or brexpiprazole for 3 weeks. Subjects will receive a starting dose of 2 mg/day of brexpiprazole (or corresponding placebo) from Days 1 to 3, followed by titration to 3 mg/day brexpiprazole (or placebo) on Day 4. Further dose increases up to 4 mg/day may occur no earlier than Day 7 at the investigator's discretion based on treatment response. Subjects who are unable to tolerate their current dose can be titrated down at any time to a minimum of 2 mg/day. Subjects may be re-titrated back to higher dose levels based on investigator discretion. Dose adjustments must be made in increments of 1 mg/day. Subjects who are unable to tolerate 2 mg/day brexpiprazole will be discontinued from the trial. All subjects will remain hospitalized for a minimum of the first 2 weeks of the 3-week treatment phase. However, subjects who, in the opinion of the investigator, have clinically improved from their baseline assessments with mild to no manic symptoms, and are stable enough to be treated on an outpatient basis, including no risk of suicide as assessed by the Columbia-Suicide Severity Rating Scale (C-SSRS), may be discharged and will continue as outpatients for the last week of double-blind treatment. Subjects who do not meet these criteria will remain hospitalized for the duration of the 3 week treatment phase.

A drug screen and alcohol test are required at the Day 21/Early Termination (ET) visit for subjects who are discharged from the hospital at the end of Week 2 (Day 14) to verify continued compliance with the protocol.

Follow-up Phase: If any subject discontinues the trial early, every effort should be made to complete the Day 21/ET assessments as soon as possible and prior to starting any new medication or treatment. Subjects who complete all trial visits through the Day 21 visit and had no major protocol violations may be offered entry into an optional open-label

rollover trial. Subjects who do not enter the open-label trial will be followed up for safety reasons via telephone contact or in clinic visit 21 (\pm 2) days after the last dose of IMP. This contact also applies to subjects who are withdrawn prematurely from the trial.

C-SSRS = Columbia-Suicide Severity Rating Scale.

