3.7.1.7 End of Treatment Phase - Day 21/Early Termination Visit

All subjects will undergo a complete evaluation at Day 21 (\pm 2 day). In addition, Day 21 evaluations are to be completed for any subject withdrawn at any time after randomization into the trial. Attempts should be made to complete all evaluations, particularly efficacy assessments, for the Day 21/ET visit prior to the administration of any new psychotropic medications. However, if the subject receives a new rescue medication for worsening manic symptoms prior to ET procedures prior to the Day 21/ET procedures, no efficacy assessments should be performed.

The following procedures will be performed on Day 21 (\pm 2 day) or the ET visit:

- A qualified and certified rater will administer the YMRS, CGI-BP, CCI [REDACTED]

- The investigator (or qualified designee) who is adequately trained will complete the “Since Last Visit” C-SSRS form.
- CCI [REDACTED]
- A complete physical examination will be performed.
- Vital sign measurements (body weight, body temperature, blood pressure, and heart rate) will be recorded. Blood pressure and heart rate are to be measured in the following order: supine and standing after the subject has been in each position at least 3 minutes.
- A standard 12-lead ECG will be performed after the subject has been supine and at rest for at least 5 minutes.
- Blood samples for clinical laboratory tests (hematology, coagulation parameters, and serum chemistry, including prolactin, HbA1c, and thyroid-stimulating hormone [TSH] with reflex to T₄ if the result for TSH is abnormal) must be drawn after a minimum 8-hour fast.
- Samples will be obtained for blood alcohol testing.
- Urine will be collected from subjects for urinalysis and urine screen(s) for drugs of abuse.
- A urine pregnancy test will be performed for all WOCBP. All positive results must be confirmed by a serum pregnancy test.
- CCI [REDACTED]
- CCI [REDACTED]
- Adverse events and concomitant medications will be recorded.
- Trial personnel will access the IWRS or equivalent to register the visit.
- Drug accountability will be performed.

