3.8.3.2 Treatment Discontinuation

After randomization, a subject may stop treatment permanently for a variety of reasons. Treatment discontinuations may be initiated by a subject who is not satisfied with treatment or may become medically necessary due to AEs, required treatment with a disallowed medication or therapy, or other issues, as determined by the investigator. However, each investigator must comprehensively review the circumstances and offer the subject options for continued treatment to the degree possible as described in [Section 3.8.3.5](#).

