3.8.3.4 Withdrawal of Consent

All subjects have the right to withdraw their consent from further participation in the trial at any time without prejudice. Subjects cannot withdraw consent for use of data already collected as part of the trial, but only for future participation. The investigator can also discontinue a subject's participation in the trial at any time if medically necessary.

Unless the subject provides their written withdrawal of consent or there is other written documentation by the investigator confirming the subject's verbal intent to completely withdraw from the trial, subjects should be followed for all protocol-specified evaluations and assessments, if possible.

Complete withdrawal of consent requires a subject's refusal of ALL of the following methods of follow up (these methods of follow up will also be noted in the trial ICF):

- Participation in all follow-up procedures specified in the protocol (whether in-clinic, by telephone, or by an in-home visit).
- Participation in a subset of protocol specified follow-up procedures (by a frequency schedule and method, as agreed by subject and staff).
- Contact of the subject by trial personnel, even if only by telephone, to assess current medical condition, and obtain necessary medical or laboratory reports relevant to the trial's objectives.
- Contact of alternative person(s) who have been designated in source records as being available to discuss the subject's medical condition, even if only by telephone, mail, or e-mail (eg, family, spouse, partner, legal representative, friend, neighbor, or physician).
- Access to medical information from alternative sources (eg, hospital/clinic medical records, referring doctor's notes, public records, dialysis, transplantation or vital registries, social media sources).

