3.10 Definition of Completed Subjects

The treatment period is defined as the time period during which subjects are evaluated for primary and/or secondary objectives of the trial irrespective of whether or not the subject actually consumed all doses of the IMP. Subjects who are evaluated at the last scheduled visit during the treatment period will be defined as trial completers. For purposes of this trial, subjects who complete Day 21 visit will be defined as trial completers.

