8.1.1 Primary Efficacy Analysis

[figure not shown]
The objective of the primary analysis is to demonstrate the efficacy of brexpiprazole for the acute treatment of manic episodes, with or without mixed features, in subjects with a diagnosis of bipolar I disorder.

The estimand for the primary efficacy analysis is the difference in outcome improvement if all subjects tolerated and adhered to their treatment. This approach is Estimand #3 recommended by the 2010 National Academy of Sciences' National Research Council report on prevention and treatment of missing data and ICH E9 (R1) "Addendum to Statistical Principles for Clinical Trials on Choosing Appropriate Estimands and Defining Sensitivity Analyses in Clinical Trials".

[figure not shown]
This estimand focuses on the efficacy of brexpiprazole in change from the baseline in YMRS Total Score. The objective of this trial is consistent with the election of an efficacy rather than effectiveness estimand.

The primary analysis will be performed on the Efficacy Sample which includes all randomized subjects who took at least 1 dose of IMP in the double-blind treatment phase and who have both a baseline value and at least 1 post-randomization YMRS Total Score during the double-blind treatment phase. The primary efficacy analysis will be performed by fitting a mixed-effect model repeated measure (MMRM) analysis with an unstructured variance covariance structure in which the change from the baseline in YMRS Total Score during the

double-blind treatment phase will be the dependent variable based on the observed cases (OC) data set. The OC data set will consist of actual observations recorded at each visit during the double-blind treatment phase and no missing data will be imputed. **CCI**

CCI

8.1.3.2

CCI

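### On the visible text, the SAP's 7-day post-dose allowance lets ratings made on another antipsychotic or mood stabiliser into an adherence-based primary analysis, and its adverse-event tables mix on-treatment with post-dose events (low severity, cheap to fix)

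*SAP*

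**What the plan says.** **Efficacy.** SAP 8.1.1 defines the target: "The estimand for the primary efficacy analysis is the difference in outcome improvement if all subjects tolerated and adhered to their treatment". It calls this an efficacy rather than an effectiveness estimand and fits an MMRM to observed cases. SAP 10.1 assigns scheduled and early-termination (ET) ratings to four windows: Days 2-5, 6-10, 11-17 and 18-24. It adds two rules:

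- "Evaluations occurring more than 7 days after the last double-blind dosing date will not be mapped into study visit windows"
- "If more than one observation falls within a particular study day interval, then the last observation within that interval is used"

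The protocol keeps some subjects under assessment after they stop drug. Unless consent is fully withdrawn, "subjects should be followed for all protocol-specified evaluations and assessments, if possible" (Protocol 3.8.3.4). The treatment period runs "irrespective of whether or not the subject actually consumed all doses of the IMP" (Protocol 3.10). Reasons for stopping include "required treatment with a disallowed medication or therapy" (Protocol 3.8.3.2).

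Two passages limit late ratings. Protocol 3.1 wants ET assessments "as soon as possible and prior to starting any new medication or treatment". Protocol 3.7.1.7 says that no efficacy assessment should be made "if the subject receives a new rescue medication for worsening manic symptoms" before the Day 21/ET procedures. For other new psychotropics, that section asks only that attempts be made to rate first.

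**Adverse events.** SAP 9.1 describes its incidence tables as covering the double-blind treatment period, yet includes events up to 30 days after the last IMP day. Protocol 5.7 follows events to 21 (+2) days. Footnote c of Protocol Table 3.7-1 gives the follow-up contact only to subjects who do not enter the open-label trial.

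**The concern.** The estimand is defined by adherence, but the mapping rule is defined by time since the last dose. No visible SAP rule asks whether the subject had started another active drug when rated. A rating made on another antipsychotic or mood stabiliser says little about brexpiprazole or placebo under adherence, yet it can serve as the Day 14 or Day 21 value in the primary and key secondary models. It can also displace an earlier rating in the same window.

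For safety, one table combines events during dosing with events after it. Post-dose ascertainment also depends on whether the subject rolled over, which is settled after randomisation. A reader cannot tell whether an event after the first open-label dose would count under the randomised arm.

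**Working it through.** **1. Which ratings can enter.** A rating on day t after a last dose on day L is mapped if t − L ≤ 7 and t lies in a window (SAP 10.1).

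| Window | Earliest last dose that can supply it |
|---|---|
| Day 21 (18-24) | 18 − 7 = Day 11 |
| Day 14 (11-17) | 11 − 7 = Day 4 |
| Day 7 (6-10), Day 4 (2-5) | Day 1 |

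A last dose on Day 10 with a rating on Day 18 has a lag of 8 and is excluded, so the rule does bind.

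**2. The switched-drug route.** Suppose a subject stops on Day 8 for an adverse event, starts another antipsychotic on Day 9 and is rated on Day 14. The lag is 14 − 8 = 6 ≤ 7, and Day 14 lies in 11-17. The bar in Protocol 3.7.1.7 does not apply, because the new drug was not rescue for worsening mania. The rating enters the model.

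**3. Completers.** IMP is dispensed through Day 21 (Protocol 3.7.1.6), and the visit may fall on Days 19-23. The largest lag is 23 − 21 = 2 days. Any shorter limit must therefore be at least 2 days.

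**4. Recall period.** The YMRS script asks about the past week, and CGI-BP severity covers the past seven days (Protocol Appendices 7 and 9). At a lag of 7 days, 6 of the recall days are undosed, or 7 if the rating day is counted.

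**5. Size.** The planned effect and SD are redacted, so the stated 90% power with 152 per arm cannot be reproduced from its inputs. Working backwards, a two-sample t-test at two-sided 0.05 with 152 per arm has 90% power at a standardised effect of 0.373.

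Assume a share s of Day 21 ratings in each arm is affected, and that those ratings keep a fraction r of the between-arm difference. The effect becomes 0.373 × [1 − s(1 − r)].

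| Assumed s | Ratings of 304 | Power, r = 0.5 | Power, r = 0 |
|---|---|---|---|
| 1% | 3 | 89.7% | 89.4% |
| 2% | 6 | 89.4% | 88.8% |

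At 2% the loss is 90 − 89.4 = 0.6 to 90 − 88.8 = 1.2 points. A 2-point loss needs 6.6% affected (20 of 304) at r = 0.5, or 3.3% (10 of 304) at r = 0.

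**6. Adverse-event window.** The follow-up contact falls on post-dose days 19-23. The part of the 30-day window after that contact is 30 − 23 = 7 to 30 − 19 = 11 days, or 23% to 37% of it. For a completer who does not roll over, the post-treatment share of observed days is 19/(21 + 19) = 48% to 23/(21 + 23) = 52%. These figures describe days, not events or bias.

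**The case against.** **Unseen text.** Footnote b sits on the Day 18-24 window, which holds the primary time point, and its wording is not visible. Section 10.2 and parts of 8.1 and 9.1 cannot be seen either, and the SAP's references on informative dropout and pattern-mixture models suggest that missing-data analyses are among the redacted text. A reader might infer that the SAP has no rule at all; the documents support only that none is visible. This stands, and it makes checking those parts the first step.

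**The 7-day limit is reasonable.** It is pre-specified and matches the recall period of both scales. A reader might infer that every off-drug rating should go, or that an on-drug rating should always win within a window. The documents do not require that. Counting only ratings up to the last dose as on-drug would hold dropouts to a lag of 0 while completers are allowed 2 days. It could also discard the ET rating that shows why the subject stopped, which an observed-cases MMRM needs. This stands: the limit and the last-in-window rule should remain in the primary analysis.

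**The route is narrow.** Psychotropics are prohibited during the trial, apart from limited exceptions such as oral lorazepam. ET ratings are due promptly and before new treatment, and subjects are inpatients for at least two weeks. The example in step 2 needs a late ET rating made after new treatment, contrary to what Protocol 3.1 asks. This stands as to frequency, but that request is best effort and the SAP does not enforce it.

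**Rollover.** A reader might infer that open-label events contaminate the randomised comparison. That is not shown. Rollover subjects get no follow-up contact in this trial, so later events may never reach its database. The 30-day rule may also usefully capture later IMP-related serious events reported under Protocol 5.7.3. What remains is a missing cutoff and a mismatch between 30 and 21 (+2) days.

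**Conclusion.** The point holds as a low-severity gap. On the visible text, the adherence estimand and the visit-window rule do not fully agree: a rating made on another antipsychotic or mood stabiliser can enter the primary and key secondary MMRM when the drug was not rescue for worsening mania. The number of such ratings is unknown and probably small. The 0.6 to 1.2 point loss rests on an assumed 2% share, equal in both arms, half to none of the difference retained, and a two-sample approximation to the MMRM. The calculation shows dilution only and gives no evidence of a false-positive risk. The reason to act is that the estimand and the data rule should agree before unblinding.

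For adverse events, the mismatch between the SAP's 30 days and the protocol's 21 (+2) days is plain in the text, and on-treatment and post-dose events share a table. No collected data are lost and no contamination is shown. Both parts depend on the unseen text being silent.

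**What to change.** Read footnote b, Section 10.2 and the redacted parts of SAP 8.1 and 9.1. If they are silent:

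1. **SAP 8.1.1 and 10.1.** Exclude from the primary and key secondary MMRM any rating made after the first dose of a new antipsychotic or mood stabiliser. Apply this before the last rating in a window is chosen. The dates should be available, because footnote e of Protocol Table 3.7-1 has all medications during the trial recorded. Report the number of ratings removed by arm.
2. **Primary rule otherwise unchanged.** Keep the 7-day limit and the last-in-window rule. Add one supportive MMRM with a shorter pre-specified limit, not below 2 days, so that completers' Day 19-23 visits stay in.
3. **SAP 9.1.** Tabulate on-treatment and post-treatment adverse events separately, as SAP 9.8 already does for concomitant medications. End the window at the first open-label dose for rollover subjects. Reconcile 30 days with 21 (+2) days, and still report later IMP-related serious events.

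The cost is SAP wording, one more model run, one count by arm and one split table. The downside is slightly more missing data among dropouts, and the count by arm shows whether the removals are unbalanced.
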